## STATISTICAL DESIGN AND POWER

**Aim 1. Power calculation.** Goren et al. demonstrated a significant difference in ED utilization by caregiver status (7.2% for caregivers vs. 4.0% for non-caregivers). Assuming a two-tailed test and a proportion of 4% experiencing ED use in the non-caregiver group, we will have 99% power to detect a relative risk of 1.8 for ED utilization among caregivers vs. non-caregivers. This is likely an underestimate, given that individuals with obesity have a greater use of hospital services, and incidence is likely to be higher in our cohort.

**Aim 1. Statistical analyses.** We will explore post-donation ED use by caregiver status, using generalized estimating equations (GEE) accounting for repeated measurements, to estimate whether odds of ED use differ by caregiver status. We will use Poisson regression to explore count of ED visits among those who report having used these services by caregiver status, adjusting for baseline characteristics, including demographic, socioeconomic, and health status at donation. We will explore the presence of effect modification and interaction between caregiving status and donor age, race/ethnicity, and rurality. As a sub-aim, we will explore whether utilization differs by self-reported physical, mental, and financial burden among caregiver donors.

**Aim 2. Power calculation.** Goren et al. demonstrated a significant difference in the proportion of Alzheimer's caregivers experiencing hospitalization (8.1% for caregivers vs. 5.1% for non-caregivers). Assuming a two-tailed test and a proportion of 5% experiencing hospitalization in the non-caregiver group, we will have 99% power to detect a relative risk of 1.6 for hospitalization among caregivers vs. non-caregivers. This is likely an underestimate, given that this study was performed in Japan, and hospital admissions for many preventable diseases are higher in the United States than in other countries.

**Aim 2. Statistical analyses.** We will explore odds of post-donation hospitalization by caregiver status, first using generalized estimating equations to account for repeated measurements, then using Poisson regression to explore the counts of hospitalization among those who report having used these services. As in Aim 1, we will explore the presence of effect modification and interaction by stratification and interaction terms between caregiving status and donor age, ethnicity, and rurality, in addition to exploring the role of self-reported burden in hospitalization among the subset of caregiver donors.

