**Title: Healthcare Utilization in Obese Caregiver Living Donors**

**NCT04341896**

**Date: December 16, 2024**

**Study Protocol and Statistical Analysis Plan (with Results)**

## PROTOCOL

**Study population.** 25,352 donors from 278 centers will be studied. Contact information for donors was provided by the Scientific Registry of Transplant Recipients (SRTR) and is verified using Lexis Nexis Accurint. We anticipate that approximately 20% (n=5,070) of this cohort will have served as the primary caregiver for their recipient. Characteristics of the overall cohort and the subset of caregiver donors are in Table 1. Moreover, the subset of caregivers > 50 years is greater than the whole cohort, further highlighting the need for aging research in this population.

Table 1. Characteristics of obese living donors

	1R01DK113980 (Overall cohort) (n=25,232)	Subset of caregiver donors (n=5,070)
Age in years, median (IQR)	41 (33-49)	46 (39-53)
Age 50+ years, %	23.8	38.6
Female, %	58.4	65.0
Minority race/ethnicity, %	18.5	17.0

**Donor questionnaire.** All participants are contacted through a centralized phone bank maintained by the parent R01's PI at UAB and are administered a survey by phone, mail, or email. The following data are collected and maintained using a robust, redundant, secure, web-based computer entry system (REDCap): demographics (gender, date of birth, race/ethnicity); socioeconomic (education, employment, marital status); family history of comorbid disease; follow-up (frequency of doctor visits pre and post-donation); comorbidities pre and post-donation (smoking, cardiovascular disease, diabetes, etc.), current hypertension, diabetes, or chronic kidney disease/end-stage renal disease, and mental health quality of life. Patients are contacted for follow-up surveys annually. Furthermore, we will leverage the infrastructure of the parent R01 to collect new primary data specific to caregivers. Among those who were the primary caregivers for their recipients, we will administer additional questions derived from the Bakas Caregiver Outcomes Scale and National Alliance for Caregiving quantitative interviews, to describe their physical and mental health at time of donation, including self-reported caregiver burden and benefit pre and post-donation, the economic impact of caregiving, and the caregiving role in the context of donation.

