**Medical records abstraction.** During completion of the questionnaire, donors are asked to provide signed waivers for medical records requests from their primary and other care providers. Pre-donation medical records are obtained from the transplant center. Post-donation medical records are obtained from the transplant center, as available, and from the participants' medical providers over time.

**Aim 1: To assess emergency department utilization associated with caregiving among a cohort of living kidney donors who were obese at the time of donation.** We will leverage an existing multi-center R01 study of a national cohort of obese living kidney donors, to quantify the association between a donor reporting that they served as the primary caregiver for the transplant recipient and ED utilization using generalized estimating equations. We will adjust for baseline characteristics and will explore the presence of effect modification and interaction between caregiving status and donor age, race/ethnicity, and rurality.

**Study population.** The study population will consist of living donors with obesity identified by the parent R01, categorized by whether or not they served as the primary caregiver for their transplant recipient. Donors will be stratified by relationship to the recipient (parent, child, spouse/life partner, other caregiver) and sex to allow us to explore sex as a biological variable. We estimate that approximately 20% (n=5,070) were the caregiver for their recipient, of whom 40% were  $\geq 50$  years old (3%  $> 65$  years), and 17% were minorities.

**Definition of caregiver.** Donors are asked whether they served as the primary caregiver (i.e., the main individual who provided unpaid caregiving activities pre and post-donation) for their transplant recipient.

**Definition of outcome of interest.** As part of the parent R01, healthcare utilization data are obtained from the questionnaire and include whether donors have utilized the ED since donation. Donors are asked to report not only whether they used the ED as well as the frequency of use.

**Aim 2: To assess hospitalization associated with caregiving among a cohort of living kidney donors who were obese at the time of donation.** We will use the same cohort from Aim 1 to quantify the association between a donor reporting that they served as the primary caregiver for their transplant recipient and hospitalization using generalized estimating equations.

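### Both GEE analyses allow for repeated surveys within a donor but not for transplant center, so at the planned size the caregiver intervals may be too narrow if caregiver share and utilization both vary by center

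*Combined protocol and SAP*

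**What the plan says.** The Study population paragraph of the PROTOCOL section states that "25,352 donors from 278 centers will be studied" and, on caregivers, "We anticipate that approximately 20% (n=5,070) of this cohort will have served as the primary caregiver for their recipient". Exposure is recorded donor by donor: "Donors are asked whether they served as the primary caregiver" (Definition of caregiver).

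Under STATISTICAL DESIGN AND POWER, Aim 1 compares the odds of ED use by caregiver status "using generalized estimating equations (GEE) accounting for repeated measurements". Aim 2 treats hospitalization likewise, "first using generalized estimating equations to account for repeated measurements". Each aim adds a Poisson model for the number of events among users, with no statement about correlation. The Aim 1 covariates are described as "adjusting for baseline characteristics, including demographic, socioeconomic, and health status at donation". Center is not in that list, and neither aim gives it any other role. The plan also does not name the GEE cluster identifier, the working correlation or the variance estimator.

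**The concern.** The only dependence that the plan names is between surveys of the same donor. Read plainly, donors from one center are treated as independent of each other. They may not be: they can share a region and local access to care, and centers can differ in the mix of donor-recipient relationships, which in the RESULTS section is strongly related to caregiver status (50.0% of caregivers were spouses, against 7.9% of non-caregivers). The plan itself examines rurality as an effect modifier, so it already allows that place may matter.

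Where exposure and outcome both vary by center, a donor-level variance is too small. Confidence intervals for the caregiver odds ratios and rate ratios would then be too short, and the actual type I error would exceed its nominal level.

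**Working it through.** **1. The plan's own figure.** For ED use, with a two-sided test and a 4% rate in the comparison group, the plan claims: "we will have 99% power to detect a relative risk of 1.8 for ED utilization". Alpha is not stated, so I take it as 0.05. With 5,070 caregivers and 25,352 − 5,070 = 20,282 non-caregivers, a two-proportion calculation gives power above 99.99% for ED use (4.0% vs 7.2%) and for hospitalization (5.0% vs 8.0%). The stated 99% is therefore reproduced, conservatively. Using the Table 1 total of 25,232 changes nothing.

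**2. Donors per center.** Planned: 25,352 / 278 = 91.2. Reported: 784 / 278 = 2.8, assuming that all 278 centers contribute.

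**3. Formula.** Caregiver status varies within center, so the variance inflation is

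D = 1 + (m − 1) × ICC of exposure × ICC of outcome,

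where m is donors per center, multiplied by (1 + CV²) if center sizes are unequal (CV is the coefficient of variation of center size). The true standard error (SE) is √D times the donor-only SE, and the actual two-sided alpha is 2 × [1 − Φ(1.96/√D)].

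**4. Planned cohort.** All ICCs and the CV are assumptions; the documents give none.

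| ICC exposure / outcome | D, equal sizes | √D | Actual alpha | √D, CV = 1 |
|---|---|---|---|---|
| 0 / any | 1.000 | 1.000 | 5.0% | 1.000 |
| 0.01 / 0.01 | 1.009 | 1.005 | 5.1% | 1.009 |
| 0.02 / 0.02 | 1.036 | 1.018 | 5.4% | 1.036 |
| 0.05 / 0.05 | 1.226 | 1.107 | 7.7% | 1.206 |

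For example, at 0.05/0.05: 1 + 90.2 × 0.0025 = 1.226, √1.226 = 1.107, and 1.96/1.107 = 1.77, which gives alpha 7.7%.

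**5. Simulation check.** This used 278 centers, CV of center size 1, one observation per donor and 1,500 replicates per scenario.
- With no center variation in caregiver share, donor-only type I error was 4.8% to 5.4%, even at an outcome ICC of 0.05.
- With both ICCs at 0.05, the true SE was about 1.2 times the donor-only SE and type I error was about 10%.
- With center-clustered variance, type I error was about 5% to 6% in nearly all scenarios (range 4.1% to 6.8%). The Monte Carlo SE is √(0.05 × 0.95/1,500) = 0.6 percentage points.

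**6. Reported cohort.** With m = 2.8, both ICCs at 0.05 give √D = 1.002, or 1.006 at CV = 1. The largest value on the grid examined (exposure ICC 0.10, outcome ICC 0.05, CV = 1) is 1.012. Simulated donor-only type I error stayed at about 4% to 6%.

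**7. Effect on power.** Dividing both group sizes by a design effect of 2, which exceeds every value above, leaves power at 99.998% for ED use and 99.97% for hospitalization.

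**The case against.** The strongest reply is that the consequence is conditional and the documents do not establish the condition. Narrowing needs both ICCs to be above zero, and neither is given. Caregiver status is each donor's own report and follows kinship; nothing ties it to center practice. The outcomes come from a questionnaire run by one central call operation, not by the centers. Adjustment for patient characteristics, and the rurality terms, may absorb some geographic variation. This stands. It is why the point says may, and why no single figure can be given.

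The reply also notes that 91 per center is a ceiling, since it requires every planned donor to be analysed. If 20% responded (an assumption), m would be 18.2. Both ICCs at 0.05 would then give D = 1 + 17.2 × 0.0025 = 1.043, √D = 1.02 and alpha about 5.5%. This stands too. The plan is nevertheless written for the full cohort.

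Finally, because the plan names no cluster identifier or variance estimator, a donor-level variance is inferred from the mention of repeated measurements alone. That is fair, and it is a reason to state the clustering explicitly.

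A reader might go further and apply the cluster-randomized design effect, 1 + (m − 1) × ICC, which gives 1.9 at an ICC of 0.01 and 5.5 at 0.05. That formula is for an exposure that is constant within center. Caregiver status is reported by each donor and varies within center, so the documents do not support it.

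**Conclusion.** The omission is real: both aims name only within-donor correlation, and center has no role in either model. The consequence is possible but not established. At the planned size with equal center sizes, the donor-only SE is correct if caregiver share does not vary by center. The true SE is about 2% larger at ICCs of 0.02/0.02 and about 11% larger at 0.05/0.05. Unequal center sizes raise these to about 4% and 21% at a CV of 1.

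Two stronger readings are not supported. A reader might infer that the stated power fails; it does not, because the margin is very large. A reader might also infer that the reported findings are undermined. Spread over 278 centers, the 784 donors give an effect of about 1% or less, and the RESULTS section gives no GEE odds ratio or interval to correct. The documents do not say how many centers those 784 came from.

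This is a low-priority improvement, worth making because it is cheap.

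**What to change.** In the Aim 1 and Aim 2 statistical analyses paragraphs, state that the transplant center is the cluster for the robust (sandwich) variance, with a donor's repeated surveys nested within center. Apply this to both the odds models and the Poisson count models. Report how many centers contribute to each analysis, and use a small-sample correction to the sandwich variance if they are few.

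The cost is one line of specification. Center should already be held for each donor, since pre-donation records come from the transplant center. The downside is slightly wider intervals where center correlation exists, and almost no change where it does not.

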**Study population.** The same study population identified in Aim 1 will be used.

**Definition of outcome of interest.** The parent R01 also captures data on whether the donor has been hospitalized since donation and the number of times the donor has been hospitalized.

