## RESULTS

Among 784 donors (median 10.4yrs post-donation), 148 (18.9%) identified as caregivers. Caregiver donors were older (62.6 vs. 57.9yrs,  $p < 0.001$ ), more often female (69.6% vs. 58.3%,  $p=0.01$ ), the recipient's spouse (50.0% vs. 7.9%) or parent (16.2% vs. 4.6%,  $p < 0.001$ ), and retired (38.4% vs. 24.9%,  $p=0.004$ ), with no racial differences. Among those identifying as the caregiver and responding to the question about hospitalization ( $n=138$ ), 71 (51.5%) reported having been admitted to the hospital since donation, compared to 237 (40.3%) among non-caregivers. Among those identifying as the caregiver and responding to the question about emergency room utilization since donation ( $n=144$ ), 77 (53.5%) reported having been admitted to the hospital since donation, compared to 305 (49.4%) among non-caregivers.

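### The users-only Poisson count step in both aims states no variance that suits truncated or repeated counts, so its standard errors are generally wrong

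*Combined protocol and SAP*

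**What the plan says.** Under STATISTICAL DESIGN AND POWER, each aim has two steps.

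- **Any use.** Aim 1 analyses ED use "using generalized estimating equations (GEE) accounting for repeated measurements, to estimate whether odds of ED use differ by caregiver status". Aim 2 models the odds of hospitalization "first using generalized estimating equations to account for repeated measurements".
- **Counts among users.** Aim 1: "We will use Poisson regression to explore count of ED visits among those who report having used these services by caregiver status", with adjustment for baseline characteristics. Aim 2: "then using Poisson regression to explore the counts of hospitalization among those who report having used these services".

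The data behind the counts are described in the PROTOCOL section. On ED visits: "Donors are asked to report not only whether they used the ED as well as the frequency of use". For Aim 2 the parent study records "the number of times the donor has been hospitalized". On timing: "Patients are contacted for follow-up surveys annually".

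Neither statistical paragraph gives a variance estimator, a dispersion check, a truncated likelihood or a clustering rule for the count step. Neither says whether a donor contributes one count or several. RESULTS reports any use only and gives no count analysis.

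**The concern.** Model-based Poisson standard errors are valid when the variance of the count equals its mean. Once the analysis keeps only donors with at least one event, that equality no longer follows even if the underlying visits are exactly Poisson: dropping the zeros raises the mean and shrinks the variance relative to it. Over-dispersion, which is common in utilization data, pushes the other way. The standard error is right only where the two happen to cancel.

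Repeated measurements raise a second issue. The plan attaches its repeated-measures handling to the odds step, and in Aim 2 the order is GEE first, Poisson afterwards. If several annual records per donor enter the count model, nothing stated accounts for their correlation.

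At stake are the confidence intervals and p-values for the caregiver comparison of visit and admission counts. The users-only target is not at fault: any use first, then counts among users, is a legitimate two-part structure, and the plan is open about it.

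**Working it through.** **The plan's own figure.** The only stated figure is 99% power for any use; there is none for the count step. Take 5,070 caregivers, 25,352 − 5,070 = 20,282 non-caregivers, and a two-sided 5% level (assumed; not stated).

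- Aim 1, 4.0% vs 7.2%: SE = √(0.04×0.96/20,282 + 0.072×0.928/5,070) = 0.00388; 0.032/0.00388 = 8.24, far above 1.96.
- Aim 2, 5% vs 8%: SE = √(0.05×0.95/20,282 + 0.08×0.92/5,070) = 0.00411; 0.03/0.00411 = 7.31.

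Power exceeds 99.99% in both aims, so the stated 99% is met. It concerns any use and is untouched by what follows.

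**Inputs for the count step, from RESULTS.**

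- Hospitalization: "71 (51.5%) reported having been admitted to the hospital since donation, compared to 237 (40.3%) among non-caregivers". Users are 71 vs 237; non-caregiver use rate p = 0.403.
- ED: users are 77 vs 305; p = 0.494. The ED sentence in RESULTS describes these donors as admitted to hospital. I assume they are ED users, since the sentence concerns the ED question.
- Assumed: negative binomial dispersion k (k = 0 is Poisson), the same p in both groups, one count per donor, no covariates.

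**Formulas.** The underlying mean m that gives use rate p is −ln(1−p) for k = 0 and ((1−p)^(−k) − 1)/k otherwise. Among users:

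- mean μ = m/p
- variance = (m + k·m² + m²)/p − μ²
- model SE / true SE = 1/√(variance/mean)

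Worked case, ED, k = 0: m = −ln(0.506) = 0.681; μ = 0.681/0.494 = 1.379; variance/mean = 1 + 0.681 − 1.379 = 0.302; SE ratio = 1/√0.302 = 1.82.

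| Outcome | k | Users' mean | Variance/mean | Model SE / true SE | Type I error, model SE |
|---|---|---|---|---|---|
| ED | 0 | 1.38 | 0.30 | 1.82 | 0.03% |
| ED | 1 | 1.98 | 0.98 | 1.01 | 4.9% |
| ED | 2 | 2.94 | 2.42 | 0.64 | 21% |
| Hospitalization | 0 | 1.28 | 0.24 | 2.06 | 0.01% |
| Hospitalization | 1 | 1.68 | 0.68 | 1.22 | 1.8% |
| Hospitalization | 2 | 2.24 | 1.47 | 0.83 | 10% |

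Type I error is for the nominal 5% test, simulated with 20,000 runs per row and no true difference. The normal approximation 2(1 − Φ(1.96 × SE ratio)) agrees, for example 20.8% for ED at k = 2. At k = 4 the SE ratios fall to 0.29 and 0.43, and simulated error (10,000 runs) reaches 56% and 38%.

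**Break-even.** Setting variance/mean to 1 gives k = 1.02 for ED (about 1.99 visits per user) and k = 1.48 for hospitalization (about 1.92 admissions per user).

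**Cost in sensitivity when visits are Poisson (k = 0).** The model SE of the log ratio is √((1/n₁ + 1/n₀)/μ).

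- ED: √((1/77 + 1/305)/1.379) = 0.1086; true SE 0.1086/1.82 = 0.0597.
- Hospitalization: √((1/71 + 1/237)/1.280) = 0.1196; true SE 0.1196/2.06 = 0.0581.

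The ratio detectable with 80% power is exp(1.96 × SE used + 0.8416 × true SE).

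- ED: exp(0.2129 + 0.0502) = 1.30 with the model SE, against exp(2.8016 × 0.0597) = 1.18 with the correct one.
- Hospitalization: exp(0.2344 + 0.0489) = 1.33, against exp(2.8016 × 0.0581) = 1.18.

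**Clustering.** If several records per donor enter, the design effect is 1 + (records − 1) × correlation. For 2 to 5 records and an assumed correlation of 0.2 to 0.5 it is 1.2 to 3.0. Ignoring it multiplies the SE by 1/√1.2 = 0.91 down to 1/√3.0 = 0.58.

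**Do the remedies work?** In the same settings (k = 0, 1, 2), a users-only sandwich variance gives simulated type I error of 6.0% to 6.3%, nearly constant in k. A zero-truncated negative binomial likelihood-ratio test (500 runs per setting) gives 5.0% to 6.4%.

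**The case against.** Four points deserve weight.

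1. **Ordinary Poisson is inferred from silence.** The aim statements in the PROTOCOL section name GEE for ED utilization and hospitalization generally, and the ED outcome includes frequency. A Poisson GEE, usually reported with sandwich variance, is a possible reading. This stands as an ambiguity, but the statistical paragraphs do not say it, and Aim 2's sequence of GEE first and Poisson afterwards points away from it.
2. **Truncation and clustering depend on the record structure.** With one count since donation per donor, every count is at least 1 but there is nothing to cluster. With annual records from donors who ever used the service, some records can be zero. The plan does not settle this. Either way the problem remains: in the second case each donor's total is still truncated and the records are correlated. A donor-clustered sandwich variance covers both.
3. **Dispersion is unknown, and some plausible values do little harm.** The model SE is within about 10% of the true SE for k of roughly 0.83 to 1.24 (ED) and 1.24 to 1.76 (hospitalization). Covariate adjustment may also change residual dispersion. Correct, but no document shows that the data lie in those bands, and the bands differ by outcome.
4. **The step is exploratory.** It carries no power claim and no reported result. This limits the severity; it does not make the intervals right.

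**Conclusion.** The concern holds, as a minor point. Followed literally, the count rule in both aims gives standard errors that are correct only near one dispersion value per outcome. Across k = 0 to 2 they run from about twice too large to about a third too small, and the direction cannot be known from the documents. These sizes rest on the reported use rates and user numbers, an assumed negative binomial distribution, one count per donor and no covariates. Repeated records per donor would shrink the model-based errors further relative to the truth.

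The users-only contrast remains a legitimate target. One caution on reading it: neither step estimates the overall visit ratio. For crude means, the users-only ratio is the all-donor ratio divided by the any-use ratio. From RESULTS the any-use ratio is (71/138)/(237/588) = 1.28 for hospitalization (95% CI 1.06 to 1.54) and (77/144)/(305/617) = 1.08 for ED (0.91 to 1.28), where 588 = 237/0.403 and 617 = 305/0.494. The users-only ratio for hospitalization should therefore not be read as the overall ratio.

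**What to change.** Add one sentence to the statistical paragraphs of both aims: the users-only count model uses a sandwich variance clustered on donor. Alternatively, specify a zero-truncated negative binomial as the second part of a hurdle model and report the implied ratio of users' means, because its coefficient is on the untruncated scale. If several records per donor enter, that model also needs donor-level clustering. State whether one count or several annual counts per donor are used, and label the result as a contrast among users.

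Optional: a count model in all respondents, zeros included, with donor-clustered sandwich variance, the stated baseline covariates and an offset for the log of the time the question covers. In the simulations above its type I error was 5.0% to 5.7%. It answers a different question, the overall visit ratio. The outcome definitions do not clearly give the time window, so it should be taken from the questionnaire.

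The cost is that sentence and a variance option in the code, or a short reanalysis if the models have already been run. No new data are needed.

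### Both count analyses are fitted to service users only, so no planned analysis estimates visits or admissions per donor, and the users-only ratio understates that contrast when more caregivers are users

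*Combined protocol and SAP*

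**What the plan says.** Under the statistical analyses for Aims 1 and 2, each outcome is handled in two steps.

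- **Any use.** For the ED, a GEE is used "to estimate whether odds of ED use differ by caregiver status". For admissions: "We will explore odds of post-donation hospitalization by caregiver status, first using generalized estimating equations to account for repeated measurements". Neither is restricted to users.
- **Counts.** For the ED: "We will use Poisson regression to explore count of ED visits among those who report having used these services by caregiver status". For admissions: "then using Poisson regression to explore the counts of hospitalization among those who report having used these services". Both are restricted to users. The Aim 1 text adds adjustment for baseline characteristics.

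The data allow more than this. The ED outcome definition reads: "Donors are asked to report not only whether they used the ED as well as the frequency of use". The Aim 2 outcome definition says the parent study captures "whether the donor has been hospitalized since donation and the number of times the donor has been hospitalized". A donor who reports no use therefore has a known count of zero.

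The plan names no count model on all donors, no zero-truncated or hurdle distribution, and no step that joins the any-use and count results. Both power calculations concern the proportion with any use; none is given for counts.

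**The concern.** Whether a donor is a user is decided after donation and is itself the outcome of the first step. If caregiving changes who becomes a user, then caregiver users and non-caregiver users are differently selected groups. Adjustment for characteristics at donation does not undo a selection that happens later.

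The users-only ratio also answers a narrower question than the aims invite. Mean visits per donor equal the probability of any use times the mean among users, and the users-only ratio leaves out the first factor. It is the only planned use of the frequency data. A value near 1 could be read as caregivers making no more visits, when it says only that users in the two groups make similar numbers of visits.

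**Working it through.** **1. The plan's own figure.** Inputs: "25,352 donors from 278 centers will be studied"; "We estimate that approximately 20% (n=5,070) were the caregiver for their recipient"; ED use 4% against 7.2% (relative risk 1.8); hospitalization 5% against 8% (relative risk 1.6); two-tailed. Alpha is not stated, so 0.05 is assumed. Non-caregivers: 25,352 − 5,070 = 20,282. The normal approximation uses pooled variance under the null.

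- ED: z = (0.032 − 1.96 × 0.00330)/0.00388 ≈ 6.6, power above 99.99%.
- Hospitalization: z = (0.030 − 1.96 × 0.00361)/0.00411 ≈ 5.6, power above 99.99%.

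The stated 99% is reproduced as a lower bound, also with the Table 1 total of 25,232. It applies to any use only.

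**2. Identity.** With p the proportion of users and m the mean count among users (c = caregivers, n = non-caregivers):

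per-donor ratio = (p_c/p_n) × (m_c/m_n).

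The planned count model estimates m_c/m_n. Whenever p_c exceeds p_n, that ratio is smaller than the per-donor ratio.

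**3. Size under the simplest model.** Assume Poisson counts with one rate per group. Then λ = −ln(1 − p) is the mean per donor and λ/p is the mean per user. The observed proportions come from the Results section: hospitalization 71/138 = 51.4% (printed as 51.5%) against 40.3%, and ED 77/144 = 53.5% against 49.4%. The ED sentence there is worded as hospital admission and is read here as ED use.

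| Setting | p_n, p_c | λ_n, λ_c | Per-donor ratio | User means (n, c) | Users-only ratio |
|---|---|---|---|---|---|
| ED, planning | 0.040, 0.072 | 0.0408, 0.0747 | 1.83 | 1.021, 1.038 | 1.02 |
| Hospitalization, planning | 0.050, 0.080 | 0.0513, 0.0834 | 1.63 | 1.026, 1.042 | 1.02 |
| Hospitalization, observed | 0.403, 0.514 | 0.516, 0.723 | 1.40 | 1.280, 1.404 | 1.10 |
| ED, observed | 0.494, 0.535 | 0.681, 0.765 | 1.12 | 1.379, 1.431 | 1.04 |

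The direction is kept in every row, but most of the difference disappears.

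**4. When the direction could change.** From step 2, the users-only ratio is below 1 while the per-donor ratio is above 1 if m_c/m_n lies between p_n/p_c and 1. That range is 0.78 to 1 for hospitalization and 0.92 to 1 for ED at the observed proportions, and 0.63 to 1 and 0.56 to 1 at the planning proportions.

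An illustration needs three assumptions that the documents do not supply: a mean among non-caregiver users, exactly one event for each additional caregiver user, and no effect of caregiving on existing users.

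- Hospitalization, assumed mean 2.0: per donor (0.403 × 2.0 + 0.1115)/(0.403 × 2.0) = 1.14; users only (0.9175/0.5145)/2.0 = 0.89.
- ED, assumed mean 2.5: per donor (0.494 × 2.5 + 0.0407)/(0.494 × 2.5) = 1.03; users only (1.2757/0.5347)/2.5 = 0.95.

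The result is fragile. A rise among existing users of about 14% for hospitalization ((0.5145 × 2.0 − 0.1115)/0.806 = 1.14) or 5% for ED ((0.5347 × 2.5 − 0.0407)/1.235 = 1.05) brings the users-only ratio back to 1.

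**5. How much is left out.** The Results imply about 237/0.403 = 588 non-caregiver respondents for hospitalization and 305/0.494 = 617 for ED. The count models would use 71 + 237 = 308 of 138 + 588 = 726 donors (42%) and 77 + 305 = 382 of 144 + 617 = 761 (50%).

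**The case against.** The strongest reply is that the plan already asks the main question on everyone. The aims say the association is quantified by GEE, the power calculations are for any use, and the GEE keeps non-users. Modelling any use and then intensity among users is a recognised structure for utilization data. Within it, 1.02 is the correct ratio of means among users; it misleads only if read as a per-donor ratio. A reader who also sees the any-use result would see the increase in every scenario above. The count models are also worded as exploratory, although so are the GEEs in the analysis paragraphs.

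Most of this stands, and it limits the weight of the point. It does not supply what is missing: the plan does not say that the count ratio applies to users only, does not use a zero-truncated distribution, and does not combine the parts. Even a proper two-part analysis needs the combined contrast to speak about volume of use.

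A reader might infer more: that the plan discards non-users altogether, or that the count analyses will show caregivers using less care when they use more. The first is wrong because of the GEE. The second is not supported. It requires the added caregiver users to be lighter users, the documents give no mean counts, and the homogeneous Poisson model at the observed proportions gives attenuation without reversal. The Results report any-use proportions only, so no misleading count ratio has been shown.

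**Conclusion.** The point holds as a gap in what is estimated. Both count models condition on the outcome of the preceding step, and no planned analysis gives the ratio of visits or admissions per donor. That the users-only ratio is smaller than the per-donor ratio whenever caregivers are more often users is an identity and needs no distributional assumption. The sizes in the table do rest on assumptions: one Poisson rate per group, equal follow-up, no covariates, and the ED sentence in the Results read as ED use. A change of direction is a conditional possibility and should not be presented as an expected finding. The main any-use analysis is unaffected. This is a worthwhile correction to a secondary analysis.

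**What to change.** In each aim, make the caregiver count contrast a model on all donors who answered the item, with non-users entered as zero. Negative binomial regression, or a log-link model with robust variance, would serve.

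Because use is reported since donation, surveys are repeated annually and the median time since donation is 10.4 years, the model also needs:

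- the log of time since donation, or of the interval each survey covers, as offset;
- clustering by donor for repeated surveys.

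Report the ratio of visits or admissions per donor-year.

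Alternatively, keep the two-step structure as an explicit hurdle model with a zero-truncated count part, allow for follow-up time, and report the combined all-donor ratio. Under the Poisson example, the zero-truncated fit would recover the ED ratio of 1.83.

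In either case, keep the users-only means as a description of intensity among users and say that they are not an estimate of a caregiver effect.

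Cost: a short addition to the text of each aim and one extra model per aim, on data already collected.
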